6.3.1 Inclusion Criteria for Subject Selection

All inclusion criteria must be present for the patient to be eligible for enrollment.

Note: the I/E criteria refer to the patient's baseline condition prior to PCI.

General Inclusion Criteria

1. Age ≥ 18 years.
2. Patient with an indication for PCI including angina (stable or unstable), silent ischemia (in absence of symptoms a visually estimated target lesion diameter stenosis of $\geq 70\%$, a positive non-invasive stress test, or FFR ≤ 0.80 must be present), NSTEMI, or recent STEMI. For STEMI the time of presentation to the first treating hospital, whether a transfer facility or the study hospital, must be >24 hours prior to enrollment and enzyme levels (CK-MB or Troponin) demonstrating that either or both enzyme levels have peaked.
3. An attempt (whether successful or not) was made to implant a 38 mm EluNIR stent (Stent was advanced beyond the guiding catheter).

4. Non-target vessel PCI are allowed prior to enrollment depending on the time interval as follows:

a. During Baseline Procedure:

PCI of non-target vessels performed during the baseline procedure itself immediately prior to enrollment if successful and uncomplicated defined as: <50% visually estimated residual diameter stenosis, TIMI Grade 3 flow, no dissection \geq NHLBI type C, no perforation, no persistent ST segment changes, no prolonged chest pain, no TIMI major or BARC type 3 bleeding.

b. Less than 24 hours prior to Baseline Procedure:

Not allowed (see exclusion criteria #2).

c. 24 hours-30 days prior to Baseline Procedure:

- i. PCI of non-target vessels 24 hours to 30 days prior to enrollment if successful and uncomplicated as defined above.
- ii. In addition, in cases where non-target lesion PCI has occurred 24-72 hours prior to the baseline procedure, at least 2 sets of cardiac biomarkers must be drawn at least 6 and 12 hours after the non-target vessel PCI.
- iii. If cardiac biomarkers are initially elevated above the local laboratory upper limit of normal, serial measurements must demonstrate that the biomarkers are falling.

d. Over 30 days prior to Baseline Procedure:

PCI of non-target vessels performed greater than 30 days prior to procedure whether or not successful and uncomplicated.

5. Patient or legal guardian is willing and able to provide informed written consent and comply with follow-up visits and testing schedule.

Angiographic inclusion criteria (visual estimate)

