6. Target lesion(s) must be located in a native coronary artery or bypass graft conduit with visually estimated diameter of ≥ 2.75 mm to ≤ 4.25 mm.
7. Complex lesions are allowed including calcified lesions (lesion preparation with scoring/cutting and rotational atherectomy are allowed), presence of thrombus, CTO, bifurcation lesions, ostial RCA lesions, tortuous lesions, bare metal stent restenotic lesions, protected left main lesions, and saphenous vein graft lesions.
8. Overlapping stents are allowed as long as the first stent implanted is the EluNIR 38 mm long stent

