6.3.4 Point of Enrollment

Given the relatively low incidence of PCI to long lesion (8.4% in the ADAPT-DES trial), and the fact that the EluNIR 38 mm stent is approved and marketed in Israel, patients will be consented after PCI. Once a patient has met all general and angiographic eligibility criteria, a 38 mm long EluNIR stent been passed beyond the guiding catheter, and the patient has signed an informed consent (post-procedure), the patient will be enrolled into the trial. If the study stent is not advanced into the guiding catheter, the subject will not be consented and not be enrolled.

In order to minimize selection bias, all eligible patients (meeting I/E criteria and in whom a 38 mm long EluNIR stent was advanced beyond the guiding catheter) will be approached for participation in the study, regardless of final procedure outcome.

The sites will maintain a screening log of all 38 mm EluNIR stents advanced beyond the guiding catheter and document eligibility and patient consent versus refusal to participate in the study.

The screening and enrollment process is displayed in [Figure 1](#).

[figure not shown]

Figure 1: Screening and Enrollment Flow Chart

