6.4.6 Treatment Failures and Device Malfunctions

In case of failure to deliver the study stent, typical measures should be undertaken to ensure the lesion has been adequately prepared, such as use of appropriately sized pre-dilatation balloons, cutting or scoring balloons, and/or rotational atherectomy as appropriate. Guide catheter support should be optimized using standardized techniques, including use of buddy wires and/or guide extension devices as appropriate. If the study stent can still not be delivered, any commercially available stent may be used to successfully and safely complete the procedure.

All failures and EluNIR malfunctions will be documented on the appropriate CRF if the patient has been enrolled to the study. The EluNIR should be returned to Medinol for analysis and be reported in the clinical results. Instructions for returning the EluNIR are included in the trial's operations manual. Treatment failures or device malfunctions should be reported in the CRF within 24 hours, per the instructions of EDC completion.

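### Read literally, inclusion criterion 8 leaves unenrolled a patient whose 38 mm stent could not be delivered and who was completed with overlapping other stents, so that device failure would be missing from the primary endpoint

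*Protocol*

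**What the plan says.** Protocol 6.3.1 lists the inclusion criteria and adds: "All inclusion criteria must be present for the patient to be eligible for enrollment". Two of them bear on a stent that cannot be delivered.

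- Criterion 3 (general): "An attempt (whether successful or not) was made to implant a 38 mm EluNIR stent". The attempt counts once the stent has passed the guiding catheter.
- Criterion 8 (angiographic): "Overlapping stents are allowed as long as the first stent implanted is the EluNIR 38 mm long stent". The synopsis has the same wording, and 6.4.5 repeats it as a stent-use rule.

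Section 6.4.6 covers failed delivery. After the usual measures have been tried, "any commercially available stent may be used to successfully and safely complete the procedure". It sets no limit on the number of stents and does not mention overlap.

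Section 6.3.4 states that "patients will be consented after PCI". It adds that eligible patients, meaning those who meet the inclusion and exclusion criteria and in whom the stent passed the guiding catheter, "will be approached for participation in the study, regardless of final procedure outcome".

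The Full Analysis Set (FAS; Protocol 7.6 and 19.1, SAP 3.0) consists of enrolled subjects whether or not they received the study stent. Under Protocol 6.1.6 and SAP 3.0, patients who consented but were ineligible and are outside the FAS belong to the Safety Analysis Set. The primary endpoint is analyzed in the FAS and the per-protocol set (Protocol 7.2.2, SAP Table 2).

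**The concern.** Criterion 3, 6.3.4 and the FAS text all show an intention to count attempts that failed after the stent left the guiding catheter. Criterion 8 cuts across that intention because it asks which stent was implanted first. When the 38 mm stent was never implanted, the answer depends on how the operator completed the case. One replacement stent leaves criterion 8 untouched; two overlapping replacement stents breach it as worded.

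Eligibility would then depend on an event after the device had already failed, and every patient lost this way is a device-success failure. In a single-arm descriptive trial no control group shares the distortion. The reported proportion is itself the result, so a failure missing from the denominator raises it directly. Two sites could also classify identical failures differently, depending on how each reads the criterion.

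**Working it through.** **Following one patient through the text**

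1. The 38 mm stent passes the guiding catheter and cannot be delivered. Criterion 3 is met.
2. The operator completes the case with two overlapping commercial stents. Section 6.4.6 does not rule this out. Section 6.1.2 remarks that overlap is often needed for segments longer than a 38 mm stent, so the scenario is plausible.
3. The first stent implanted is not the 38 mm EluNIR. Read literally, criterion 8 is not met.
4. All inclusion criteria are required, so meeting criterion 3 does not waive criterion 8.
5. The patient falls outside the group that 6.3.4 says will be approached, is not enrolled and is not in the FAS. If consent was obtained anyway, 6.1.6 points to the Safety Analysis Set.
6. Device success requires a result obtained with the 38 mm EluNIR only (6.1.3.1), so this patient would have been a certain failure on the primary endpoint.

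Replace step 2 with one non-study stent, or with separate non-overlapping stents, and criterion 8 is not triggered. The patient stays eligible and, once consented, counts as a failure.

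**The plan's own figure**

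Protocol 7.1 gives 80% probability of seeing at least one device-related adverse event in 50 subjects at an incidence of 3.2%. This reproduces: 1 − (1 − 0.032)^50 = 80.3%, and the exact threshold is 1 − 0.20^(1/50) = 3.17%. The present point does not depend on it.

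**Effect of omitted failures**

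Let x be successes among n enrolled subjects and m the failures omitted. The plan reports x/n; counting the omitted cases gives x/(n + m). The upward bias is x·m / [n(n + m)]. With n = 50 and m = 1:

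- x = 45: 45/(50 × 51) = 1.8 points
- x = 48: 48/(50 × 51) = 1.9 points
- x = 50: 50/(50 × 51) = 2.0 points

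The table gives exact (Clopper-Pearson) 95% intervals. All counts are assumed for illustration.

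| Successes | m = 0 (n = 50) | m = 1 (n = 51) | m = 2 (n = 52) | m = 3 (n = 53) |
|---|---|---|---|---|
| 45 | 90.0% (78.2–96.7) | 88.2% (76.1–95.6) | 86.5% (74.2–94.4) | 84.9% (72.4–93.3) |
| 48 | 96.0% (86.3–99.5) | 94.1% (83.8–98.8) | 92.3% (81.5–97.9) | 90.6% (79.3–96.9) |
| 50 | 100% (92.9–100) | 98.0% (89.6–100.0) | 96.2% (86.8–99.5) | 94.3% (84.3–98.8) |

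**Chance that it arises at all**

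If a fraction q of attempts ends in failed delivery completed with overlapping stents, the chance of at least one in 50 attempts is 1 − (1 − q)^50. That is 39% for q = 1%, 64% for 2% and 87% for 4%. These values of q are assumptions; neither document gives one.

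**The case against.** The best reply concerns timing. Criterion 8 sits under the angiographic criteria. Section 6.4.1 bases angiographic eligibility on the angiogram obtained immediately before the procedure. Sections 12 and 13.1 confirm final eligibility from pre-stenting or pre-intervention angiography. Section 6.1.4.3 places only the general screening after the attempt. Section 6.3.1 adds: "Note: the I/E criteria refer to the patient's baseline condition prior to PCI". On this view criterion 8 restricts the intended overlap strategy and says nothing about stents used after a failed delivery. Section 19.1 also says, with no exception for overlap, that patients in whom the stent passed the guiding catheter but was not received are analyzed in the FAS.

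This reading is coherent, and a site could adopt it in good faith. It is therefore too strong to say that these patients are definitely ineligible, as a reader might infer from criterion 8 alone. But the reading does not remove the conflict. The criterion speaks of the stent implanted, whereas exclusions 28 and 29 use the word *planned* where a plan is meant. A criterion about the order of implantation cannot be judged from a baseline angiogram, and consent comes when the implanted stents are known. The FAS text, including the rule in 19.1 that keeps subjects with major deviations, helps only patients already enrolled.

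Three further points stand. The screening log in 6.3.4 covers every 38 mm stent that passes the guiding catheter, so omissions would be traceable, although no planned analysis restores them. The trial has no hypothesis test or performance goal, so no formal decision turns on the result. And a shift of about 2 points per case is small beside an interval of 78.2 to 96.7 at 45/50.

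**Conclusion.** The point holds as a conflict of wording with a known direction of bias. Read literally, criterion 8 keeps out one subset of non-deliveries, those completed with overlapping other stents, while criterion 3, 6.3.4 and the FAS definition indicate that such failures were meant to be counted. A loss occurs only if such a case arises and the site applies criterion 8 to the stents implanted afterwards. Each loss then raises the reported device success and primary endpoint by roughly 2 points at about 50 subjects.

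The total size is unknown and may be zero, because the documents give neither a non-delivery rate nor the share completed with overlap.

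A reader might also infer that all failed deliveries are lost, or that non-delivery is the main failure device success is meant to capture. The documents support neither. Completion with one stent or with non-overlapping stents leaves the patient eligible, and no passage ranks the kinds of failure.

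**What to change.** In the synopsis and 6.3.1, add to criterion 8 that it does not apply to stents placed after a failed attempt to deliver the 38 mm EluNIR. State that any otherwise eligible patient in whom that stent passed the guiding catheter remains eligible, is in the FAS if consented, and counts as a device-success failure if the 38 mm stent was not delivered.

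Add no new rule on the order of stents and leave stenting technique as it is. Because 6.4.5 repeats the overlap sentence as a stent-use rule, the sponsor should reconcile it with 6.4.6, so that completing a case after failed delivery is not also recorded as a breach.

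The cost is a short addition to the synopsis and 6.3.1 plus that reconciliation. The change affects who is counted, not how anyone is treated. The downside for the sponsor is that the reported success rate may be slightly lower.

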6.3.2 Exclusion Criteria for Subject Selection

All exclusion criteria must be absent for the patient to be eligible for enrollment.

General Exclusion Criteria

1. STEMI within 24 hours of initial time of presentation to the first treating hospital, whether at a transfer facility or the study hospital or patients in whom enzyme levels (either CK-MB or Troponin) have not peaked.

2. PCI within the 24 hours preceding the baseline procedure.
3. Non-target lesion PCI in the target vessel within 12 months of the baseline procedure.
4. History of stent thrombosis.
5. Cardiogenic shock (defined as persistent hypotension (systolic blood pressure <90 mm/Hg for more than 30 minutes) or requiring pressors or hemodynamic support, including IABP).
6. Subject is intubated.
7. Known LVEF <30%.
8. Relative or absolute contraindication to DAPT for 6 months in non-ACS patients and 12 months in ACS patients (including planned surgeries that cannot be delayed, or on or indicated for chronic oral anticoagulant treatment).
9. eGFR<30 ml/min/1.72 m²
10. Hemoglobin <10 g/dL.
11. Platelet count <100,000 cells/mm³ or >700,000 cells/mm³.
12. White blood cell (WBC) count <3,000 cells/mm³.
13. Clinically significant liver disease.
14. Active peptic ulcer or active bleeding from any site.
15. Bleeding from any site within the prior 8 weeks requiring active medical or surgical attention.
16. If femoral access is planned, significant peripheral arterial disease which precludes safe insertion of a 6F sheath.
17. History of bleeding diathesis or coagulopathy or will refuse blood transfusions.
18. Cerebrovascular accident or transient ischemic attack within the past 6 months, or any permanent neurologic defect attributed to CVA.
19. Known allergy to the study stent components cobalt, nickel, chromium, molybdenum, Carbosil®, PBMA, or limus drugs (ridaforolimus, zotarolimus, tacrolimus, sirolimus, everolimus, or similar drugs or any other analogue or derivative or similar compounds).
20. Known allergy to protocol-required concomitant medications such as aspirin, or DAPT (clopidogrel, prasugrel, ticagrelor), or heparin and bivalirudin, or iodinated contrast that cannot be adequately pre-medicated.
21. Any co-morbid condition that may cause non-compliance with the protocol (e.g. dementia, substance abuse, etc.) or reduced life expectancy to <24 months (e.g. cancer, severe heart failure, severe lung disease).

22. Patient is participating in or plans to participate in any other investigational drug or device clinical trial that has not reached its primary endpoint.
23. Women who are pregnant or breastfeeding.
24. Women who intend to procreate within 12 months after the baseline procedure (women of child-bearing potential who are sexually active must agree to use a reliable method of contraception from the time of screening through 12 months after the baseline procedure).
25. Patient has received an organ transplant or is on a waiting list for an organ transplant.
26. Patient is receiving or scheduled to receive chemotherapy within 30 days before or any time after the baseline procedure.
27. Patient is receiving oral or intravenous immunosuppressive therapy or has known life-limiting immunosuppressive or autoimmune disease (e.g., HIV). Corticosteroids are allowed.

Angiographic Exclusion Criteria (visual estimate)

28. Unprotected left main lesions $\geq 30\%$, or planned left main intervention.
29. Bifurcation lesions with planned dual stent implantation.
30. Stenting of lesions due to DES restenosis.
31. Occlusive thrombus and/or a thrombus requiring thrombectomy in a target vessel
32. Another lesion in a target or non-target vessel (including all side branches) is present that requires or has a high probability of requiring PCI within 12 months after the baseline procedure.

6.3.3 Criteria and Procedures for Subject Withdrawal or Discontinuation

6.3.3.1 When and How to Withdraw Subjects

Each enrolled subject shall remain in the trial until completion of the required follow-up period. However, a subject's participation in any clinical trial is voluntary and the patient has the right to withdraw at any time without penalty or loss of benefit. Conceivable reasons for discontinuation may include, but not be limited to, the following:

- Subject voluntary withdrawal
- Subject withdrawal by physician as clinically indicated
- Subject lost-to follow-up

The reason for subject discontinuation must be documented on the CRF and source documents. The Primary Investigators must also report all subject discontinuations to their EC as defined by their institution's procedure.

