6.3.3.2 Data to Be Collected from Withdrawn Subjects

All data from evaluations and treatments performed prior to the withdrawal should be documented on the CRFs. Source documents and angiograms that pre-date the withdrawal should be submitted

as required by the clinical investigation plan. No data that post-dates the withdrawal will be collected.

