6.3.3.3 Follow-up for Withdrawn Subjects

Once a subject has withdrawn from the trial, no further follow-up contact will be performed. However, vital status will be obtained from public records.

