4.3 General Methods

Data collected in this trial will be presented in summary tables, listings or graphs. For each parameter, the baseline value will be defined as the last non-missing value collected at the time closest to but

 Cardiovascular Research Foundation	FORM	Document N° BIO-TMP-0702 Revision: 00
	TITLE SAP Template	Effective date: 16-Mar-2018 Department: BIO

before the start of study procedure. Demographic and background characteristics, safety and efficacy data will be summarized.

Descriptive statistics will be used to generate an overall summary of the trial endpoints, baseline and procedural variables, and clinical outcomes. Continuous variables will be summarized as means, medians, standard deviations, minimums, maximums, and 95% confidence intervals for the means. Categorical data will be presented as n/N (%), percentages and exact 95% confidence intervals will be rounded and reported to a single decimal point (xx.x %). Unless otherwise noted, subjects with missing data will be excluded from the denominator.

Survival analysis techniques will be used to analyze the time-to-event variables that occur at or after 30 days of follow-up. Time to event analysis will be performed for each time point separately (i.e. up to 30 days, 6-months (180 days), 1 year (365 days)) and summarized using the Kaplan-Meier estimated event rates and number of events. Only endpoints evaluated at 30-days will be included in the primary analysis and the CSR. Analysis of clinical endpoints evaluated at 6 months and 1-year will be performed separately.

All time-to-event analyses will be performed with time defined from date of procedure to first occurrence of an event. Subjects without events will be censored at their early withdrawal date or the last known event-free time point. If this event-free time point occurs after the analysis time point, the days to event variable will be set equal to the analysis time point so that the patient will be included in the analysis (e.g. if the last data point was collected at 1 year and 2 weeks post-procedure, for the 1-year analysis, this subject will be censored at exactly 1 year (365 days)). When analyzing composite endpoints, time is measured from date of procedure to the first event (days).

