5.0 ANALYSES AND SUMMARIES

5.1 Baseline and Other Summaries and Analyses

5.1.1 Trial Conduct and Subject Disposition

The frequency and percentage of subjects enrolled by site will be provided as a table.

A tabulation of patient disposition will include the number of subjects screened, enrolled, and discontinued, with reasons for discontinuations (e.g., withdrew consent, was lost to follow-up, investigator withdrawal of subject, administrative reasons, etc.) as documented on the case report form. Adherence to trial inclusion/exclusion criteria, enrollment by site and major protocol deviations as documented on the case report form will be descriptively tabulated. A by-subject listing will include the reference data for these tables.

Compliance to 30-day follow-up visit will be summarized for all subjects in the FAS population and by site.

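### Withdrawal by a physician stops collection of non-fatal outcomes as if consent had been revoked, and the 6-month and 1-year endpoints have no sensitivity analysis for the loss

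*Protocol*

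**What the plan says.** Protocol 6.3.3.1 opens with a default: "Each enrolled subject shall remain in the trial until completion of the required follow-up period". It then lists conceivable reasons for discontinuation: the subject's own choice, "Subject withdrawal by physician as clinically indicated" and "Subject lost-to follow-up". The physician's reason has no criteria. The loss-to-follow-up reason has no minimum number of contact attempts. On recording, the section says: "The reason for subject discontinuation must be documented on the CRF and source documents". Discontinuations must also be reported to the ethics committee.

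Protocol 6.3.3.2 keeps everything recorded before withdrawal and then states: "No data that post-dates the withdrawal will be collected". Protocol 6.3.3.3 adds: "Once a subject has withdrawn from the trial, no further follow-up contact will be performed". Its next sentence makes one exception, a public-records check of vital status. Neither section separates a subject who revokes consent from one whom a physician takes out.

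The SAP expects such exits. Section 5.1.1 gives as example disposition categories "withdrew consent, was lost to follow-up, investigator withdrawal of subject, administrative reasons". For time-to-event endpoints, section 4.3 states: "Subjects without events will be censored at their early withdrawal date or the last known event-free time point".

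**The concern.** The study intervention is one stent attempt. Under Protocol 6.3.4 the subject consents and is enrolled after it. What remains is a 30-day clinic visit and two telephone contacts (Protocol 6.1.4). Leaving the trial at that stage cannot alter exposure to the device; it only removes the subject from observation.

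A subject who revokes consent must be let go. A subject taken out by a physician has not revoked anything, yet the same no-contact, no-data rule applies. If physicians tend to withdraw subjects who are getting worse, later MI, TLR, TVR and non-fatal stent thrombosis go uncollected. The trial has one open-label arm, so no comparator shares the loss. Protocol 6.3.4 takes care to limit selection at entry, by approaching all eligible patients whatever the procedural result. Nothing similar limits selection at exit.

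The rule also sits badly with the protocol's own safety text. Section 14.4 requires reported serious events and device deficiencies to be monitored until they subside or stabilise. Section 14.9.7 requires follow-up after adverse events until resolution or the end of the trial. Neither says what happens once the subject has been withdrawn.

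**Working it through.** **Inputs.**
- n = 50; 80% probability of seeing at least one device-related AE at 3.2% incidence (Protocol 7.1).
- Discontinued subjects are not replaced (Protocol 6.1.6). No dropout rate is stated.
- The 30-day MACE component includes subjects with an event and event-free subjects with at least 23 days of follow-up (SAP 4.5).
- The main primary analysis uses no imputation. Best-case and worst-case tables are planned for the primary endpoint, and no adjustment for missing data is made in any other analysis (SAP 4.4 and 5.2.2).
- Number of withdrawals, number of successes and number of 1-year events: assumptions, marked below.

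**Step 1. The plan's own figure.** 1 − (1 − 0.032)^50 = 80.3%, which reproduces the stated 80%. With 1 to 5 subjects wholly unobserved, 1 − 0.968^(50 − w) gives 79.7%, 79.0%, 78.3%, 77.6% and 76.9%. The sample-size statement is sound, and withdrawal barely moves it.

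**Step 2. Primary endpoint.** Assume 44 successes and w event-free subjects withdrawn before day 23, each of whom would have had a 30-day event. The main analysis reports 44/(50 − w). The worst case counts the missing as failures and reports 44/50. Intervals are exact (Clopper-Pearson) 95%.

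| w | Main analysis | Worst case |
|---|---|---|
| 0 | 44/50 = 88.0% (75.7 to 95.5) | 88.0% |
| 1 | 44/49 = 89.8% (77.8 to 96.6) | 88.0% |
| 2 | 44/48 = 91.7% (80.0 to 97.7) | 88.0% |

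Each such loss raises the main result by about 2 percentage points. Under this assumption the planned worst-case row gives the true figure. The bound covers subjects treated as missing. A subject withdrawn event-free from day 23 onward is analysed as event-free, so the last week of the 30 days lies outside it.

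**Step 3. Secondary endpoints at 6 months and 1 year.** Assume 3 observed events by 1 year and w subjects censored before any of those events, each of whom would later have had a non-fatal event. With no other censoring, the Kaplan-Meier estimate is 3/(50 − w), while the true rate is (3 + w)/50.

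| w | Reported | True |
|---|---|---|
| 0 | 6.0% | 6% |
| 1 | 6.1% | 8% |
| 2 | 6.3% | 10% |
| 3 | 6.4% | 12% |

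Here no planned table shows the gap. The 30-day secondary clinical endpoints use the same censoring rule over a shorter time.

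**Step 4. Passages side by side.** Section 6.3.3.2 bars all data dated after withdrawal, while 6.3.3.3 seeks vital status after withdrawal. Section 19.1 treats a death as cardiac unless a non-cardiac cause is unequivocal. The documents do not say whether a death found in public records enters MACE, TLF or TVF, or whether the subject stays censored at withdrawal.

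**The case against.** The strongest reply is that the plan already contains most of the protection needed. The worst-case table in SAP 5.2.2 bounds the primary endpoint. Events before withdrawal are kept and count. Periprocedural MI is judged within 48 hours and post-PCI biomarkers are required before discharge, so the main early events are captured before most exits. Device success is settled before enrollment. Reasons for discontinuation are documented, tabulated and listed by subject. The trial is descriptive with no performance goal, and the 6-month and 1-year results fall outside the clinical study report (SAP 1.0). All of this stands. It limits the severity but does not restore data that were never collected.

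Four stronger readings are tempting, and the documents do not support them.

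- *Withdrawal ends all data collection.* It does not: vital status continues. The loss concerns non-fatal events.
- *The bias must favour the device.* The documents do not say who would leave. If two true successes are lost from 44/50, the result is 42/48 = 87.5%, slightly against the device.
- *A subject who misses day 30 is lost and is never called again.* No section says so. Section 6.3.3.3 speaks of a subject who has withdrawn, and the default is to stay in. Listing loss to follow-up among discontinuation reasons is ordinary coding. Its place under the withdrawal heading leaves the point open, no more.
- *The protocol permits administrative withdrawal.* Section 6.3.3.1 does not list it. It appears only as an example category in the SAP's disposition table.

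It is also too strong to say that the trial only observes after the procedure, since it sets antiplatelet and contraception requirements. Those do not require that data collection stop. Section 4.6, for instance, asks only that the reason for early discontinuation of dual antiplatelet therapy be documented.

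**Conclusion.** The point holds in a limited form. The protocol states a rule under which a physician's decision, without criteria, ends collection of non-fatal endpoint data as though consent had been revoked. The rule serves no evident purpose in a trial whose device exposure precedes enrollment.

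For the primary endpoint the effect is about 2 percentage points per such subject in the main analysis, within an interval some 18 to 20 points wide, and the planned worst-case table bounds it for subjects treated as missing. The weaker spot is the 6-month and 1-year non-fatal endpoints: censored at withdrawal, with no sensitivity analysis. In the illustration, three informative withdrawals would turn a true 12% into a reported 6.4%.

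These sizes rest on assumed counts and on withdrawn subjects being those who go on to have events. That is a possibility the wording allows, not something the documents show. Severity is low to moderate: a cheap improvement.

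**What to change.** - In Protocol 6.3.3.1 to 6.3.3.3, state that only the subject's withdrawal of consent ends contact and data collection.
- State that subjects discontinued by a physician, or who miss a contact, stay in follow-up and are tried at each later scheduled contact and through hospital records.
- Reconcile 6.3.3.2 with 6.3.3.3 on vital status, and say how a death found in public records enters the endpoints.
- Reconcile 6.3.3.1 to 6.3.3.3 with 14.4 and 14.9.7 on follow-up of adverse events after withdrawal.

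The cost is protocol wording and a few tracing calls in about 50 subjects. No treatment and no sample size changes.
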